In the current phase of treatment development (Phase 2: Refining the intervention), we will perform a small (N=11) proof-of-concept trial to ensure our intervention's initial feasibility and to refine the intervention prior to a larger pilot study.

In this project, we hope to do the following:

1. Test a 10-week, telephone-delivered health behavior intervention utilizing PP exercises and systematic goal-setting in a brief, non-randomized, proof-of-concept trial (N=11).
2. Determine whether this initial intervention is feasible in a small cohort of HF patients.
3. Explore potential benefits of the intervention on outcomes of interest (e.g., optimism, positive affect).

II. SPECIFIC AIMS

Specific Aim #1 (Feasibility; primary aim): To assess the feasibility of the PP-based health behavior intervention, adherence methods, and outcome assessments in patients with NYHA class I-III HF.

Hypothesis: The PP exercises and goal-setting sessions will be feasible (i.e., 5 of the 9 exercises/sessions will be completed by a majority of patients). Furthermore, we will obtain complete objective follow-up data in at least 80% of enrolled participants at 10 weeks for both the medication and activity measurement methods.

Specific Aim #2 (Acceptability and immediate impact): To assess whether the intervention is acceptable to participants, as measured by ratings provided before and after each exercise, as well as its immediate impact on optimism.

Hypothesis: The intervention will be acceptable (mean score of at least 6 out of 10 on ratings of ease of completion and subjective helpfulness of the exercises) and will have adequate immediate impact on optimism (post-exercise ratings of optimism will be higher than pre-exercise ratings).

Specific Aim #3 (Intermediate outcomes): To assess whether this preliminary intervention appears to result in improvement of psychological well-being (as measured by dispositional optimism, positive affect, anxiety, and depression).

Hypothesis: The intervention will lead to improvements in optimism and positive affect and reductions in depression and anxiety at 10 weeks compared to baseline.

Exploratory Aim (adherence and functional outcomes): To examine the impact of the intervention on physical activity, medication adherence, sodium intake, HF-related QoL, and generic HRQoL.

Hypothesis: The intervention will lead to improvements in adherence and functional outcomes at follow-up.

III. PARTICIPANT SELECTION

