A. Inclusion/Exclusion Criteria

Inclusion criteria:

- Adult patients with NYHA class I, II, or III HF admitted to an MGH inpatient unit or outpatients at the MGH Heart Center.⁴⁹ Patients with NYHA class IV HF have ongoing HF symptoms at rest, making it difficult for them to increase physical activity and other health behaviors; therefore, they will not be included. HF diagnosis will be confirmed via chart review and with the patient's treatment team as needed. NYHA class will be confirmed with the patient and adjudicated by [name] or the patient's treatment team when necessary.
- Suboptimal adherence to health behaviors. This will be defined as a total score of ≤ 15 on three Medical Outcomes Study Specific Adherence Scale (MOS SAS)⁵⁰ items regarding diet/exercise/medications. The MOS SAS has been used in multiple prior studies assessing adherence in cardiac patients, including our own studies in this population.^{40,51,52} This threshold score on the MOS SAS will ensure that all participants will have the potential to improve their health behaviors.

Exclusion criteria:

- Cognitive deficits impeding a participant's ability to provide informed consent or participate, assessed via a 6-item cognitive test that is sensitive and specific for screening for cognitive impairment in research participants.⁵³
- Medical conditions precluding interviews or likely to lead to death within 6 months.
- Inability to speak English, inability to read or write, inability to walk, or lack of a telephone.

Justification for inclusion and exclusion criteria: We will recruit individuals over age 18 that have NYHA class I, II, or III HF and endorse suboptimal adherence to physical activity, diet, and/or medication use. We will study HF because it is extremely common¹ and has been associated with poor functioning²⁻⁵ and high rates of mortality (50% of individuals with HF die within 5 years of diagnosis).⁴ We chose NYHA class I, II, and III HF patients because class II and III patients comprise the majority of participants in studies that identify links between physical activity and improved exercise capacity, quality of life, and survival^{6,8} and because class I patients also likely would benefit from increases in physical activity and health behaviors. We did not include NYHA class IV patients

because they may be too physically impaired to perform some of the PP exercises included in the intervention.

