We will focus on adherence to health behaviors in HF for several reasons. First, adherence to health behaviors is associated with better HF outcomes, including lower rates of mortality,⁶⁻¹⁰ but patients with HF often struggle to adhere to these behaviors.^{13,14} Second, existing interventions to improve health behaviors are costly and have had limited impact on medical outcomes and quality of life.¹⁷⁻²⁰ Finally, positive psychological states have been associated with improved adherence to health behaviors in healthy and other medically ill populations,²⁶⁻³¹ suggesting that an intervention to boost these states in HF patients may be an effective way to improve these behaviors and medical outcomes in general. We will enroll only those patients who have at least mild deficiencies in health behaviors.

Exclusion criteria will include cognitive deficits, medical conditions that preclude participation in the intervention or are likely to lead to death within 6 months, inability to walk, inability to speak English, and lack of a telephone. The main purpose of these exclusion criteria is to ensure that all participants are able to fully participate in intervention procedures and provide outcome data. Children under age 18 will be excluded because they often are not directly responsible for their adherence to health behaviors (e.g., medication adherence) and because they will not be able to provide informed consent. Individuals with cognitive deficits may have difficulty recalling their affective states or providing informed consent for the study. Patients who have medical impairments that lead to a high risk of dying within 6 months likely will struggle to complete the intervention and other study procedures. Potential participants without a telephone will be unable to perform the intervention and therefore will be excluded.

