As physical activity (as measured by accelerometer) is our primary health behavior outcome measure, those patients who cannot walk will be excluded, as the accelerometers were primarily designed for step-based activities. Finally, individuals who do not speak or read English will be excluded because our current proposed interventional materials are only available in English and because it is unclear whether the intervention and study assessments could be effectively administered over the phone using interpreter services—certainly this would add an additional potential barrier to assessment and might result in inaccurate conclusions about the course of illness when in fact the language barrier/interpreter presence may have been a confounding factor. If our results suggest that the intervention is promising, we will work to expand our study to non-English-speaking populations. All potential participants will be evaluated for exclusion criteria prior to enrollment, in concert with their treatment team.

B. Sources of participants and recruitment methods

All participants will be adults with NYHA class I, II, or III HF admitted to an inpatient unit at MGH or seen as outpatients at the MGH Heart Center.

In hospital recruitment. Potential participants will be identified through daily reviews of the inpatient unit censuses and contact with (and subsequent clearance by) an inpatient team member (physician, nurse, or nurse practitioner). If a potential participant is identified, the study staff member will ask the treatment provider to inquire whether it would be okay for a study staff member to inform the patient about an optional study. If the patient were amenable, a study staff member would meet with the patient, confirm that it is okay to describe an optional study, and then discuss the study with the patient and inquire about inclusion/exclusion criteria. Interested patients will undergo cognitive evaluation (with the six-item screen), discussion of medical history to review for exclusion criteria and

confirm NYHA class, and assessment of adherence status with the MOS SAS.

Sociodemographic and medical data (age, gender, medical and psychiatric diagnoses, NYHA class, ejection fraction, alcohol consumption, and smoking history), and baseline assessments on self-report measures (including health behaviors), will be obtained at enrollment.

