- 4.) Should study staff receive no reply within 2 weeks, staff members will call the patient on the phone to assess interest in the study and to describe the study over the phone. If the patient remains interested, staff will confirm eligibility and assess for exclusion criteria. If the patient remains interested and appears eligible, study staff will set up an appointment time to go through the consent procedures and conduct the initial study visit. We will then mail or e-mail participants a consent form to look over ahead of time, so that they may prepare questions for the first visit. Note: If a participant prefers to perform all study visits by phone, a consent form will be mailed to the participant. This will be reviewed over the phone, and if the patient remains interested, he or she will sign the consent form and mail it back to study staff at MGH. Once the signed consent form is received, study staff will mail study materials to the participant, and the participant will be called for the first study visit.

For potentially eligible patients who are enrolled in the MGH Research Options Direct to You (RODY) Program, we will directly contact them via phone to inform them about the project. RODY identifies patients who are willing to be contacted directly about research studies. Patients who have agreed to be contacted directly are identifiable through the RPDR search; each patient's RODY status is available in the demographics table included in the RPDR output.

Future Studies. For participants approached either inpatient or outpatient, we will inquire at the end of the screen about whether they are interested in being contacted for future studies. This will allow us to create a database for contacting patients regarding any research studies we conduct in the future.

IV. PARTICIPANT ENROLLMENT

A. Methods of Enrollment

We will enroll participants through the recruitment procedures, described above, and the informed consent procedures, described below.

B. Procedures for obtaining informed consent

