If the patient is interested in the study after the discussion/assessment for exclusion criteria as mentioned above, a licensed physician, psychologist, social work investigator, medical student, or research assistant will approach the patient, verbally discuss the study in detail and give the patient adequate time to read a written IRB-approved consent form and to ask questions. If they desire, participants will have at least 24 hours to consider enrollment. To ensure that participants have the capacity to provide informed consent, we will ask potential participants to describe their understanding of the study's purpose and their role (e.g., that they understand the timing of intervention and its purpose, audiotaping of phone sessions and the purpose for the audiotaping, confidentiality and its limits, our focused review of medical records, and their ability to end participation in the study at any time for any reason). Patients will be given at least 24 hours if desired to consider participation in the study. In addition, patients will be informed that they will receive \$100 for completing the study (including the 10-week follow up phone call) and returning the ActiGraph GT3X+ device, mailed to them as a check at the end of the study. For tax reasons, we require a social security number in order to issue the full \$100. However, if you are uncomfortable giving that information, we can compensate you with a \$50 check without requiring your social security number. Outpatient participants who come to MGH for an initial in-person visit also will be informed that they will be reimbursed for parking.

It is exceedingly unlikely that a potential participant will be a patient currently in an investigator's clinical practice. However, if an investigator discovers that a potential participant is a member of his/her clinical practice, an alternate investigator will be substituted to provide a description of the study and obtain informed consent.

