Finally, once a participant signs the consent form, the investigator will perform a focused review of the participant's medical record (including laboratory data) to again confirm that the patient has HF, and will consult with the study cardiologist in the event that there is any need for further clarification. If there is question about the patient's medical prognosis (to assess whether the patient has a condition likely to lead to death within 6 months) the study team will consult with the patient's inpatient or outpatient team and/or the study cardiologist. Participants will be asked to sign a release form at the time of consent to allow study staff to discuss their diagnosis and aforementioned medical variables during the study.

Partners Healthcare has an electronic system that lets the participants' study doctors know if they are admitted to a Partners Hospital, or if they visit a Partners Hospital Emergency Department. We will

use this system to ensure that the study doctors know about any possible problems or side effects participants experience while taking part in the study.

C. Treatment assignment/randomization

There is no randomization procedure required for this trial.

V. STUDY PROCEDURES

A. Study visits/evaluations (See Table 1)

Initial visit (Week 1; in person). The initial visit will occur in an MGH inpatient unit, in the outpatient cardiac clinic, in a designated private office within the CPRP suite (for those contacted via opt-out letter), or over the phone (if a participant prefers to not come to the hospital for an in-person visit). Participants will meet with a member of the study staff (the study “trainer”) and complete self-report questionnaires. These questionnaires assess optimism (Life Orientation Test-Revised; LOT-R),⁵⁵ anxiety/depression (Hospital Anxiety and Depression Scale; HADS),⁵⁶ positive emotions (Positive and Negative Affect Schedule; PANAS),⁶⁵ health-related quality of life (MOS Short Form-12; SF-12),⁵⁷ cardiac symptoms and heart failure-related quality of life (Kansas City Cardiomyopathy Questionnaire; KCCQ),^{58,59} medication adherence (Self-Reported Medication Adherence [adapted from the Heart and Soul Study]; SRMA),⁶⁰ and sodium intake (Scored Sodium Questionnaire; SSQ).⁶¹ Participants will also answer questions about their alcohol (using the AUDIT-C)⁶² and cigarette use. In sum, these scales should take approximately 30 minutes to complete.

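### Does the MOS SAS pre-post comparison use a baseline score that was selected for being low?

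*Combined protocol and SAP*

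**What the plan says.** The MOS SAS items on diet, exercise and medications appear in seven places.

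- **Section III.A, inclusion criteria.** Eligibility requires suboptimal adherence: "This will be defined as a total score of ≤ 15 on three Medical Outcomes Study Specific Adherence Scale".
- **Section III.B, in-hospital recruitment.** Screening includes "assessment of adherence status with the MOS SAS". The next paragraph says that "baseline assessments on self-report measures (including health behaviors), will be obtained at enrollment".
- **Section V.A, initial visit.** The questionnaire list, which opens "These questionnaires assess optimism (Life Orientation Test-Revised; LOT-R", goes on to the HADS, PANAS, SF-12, KCCQ, SRMA and SSQ. It does not name the MOS SAS.
- **Section V.A, follow-up call.** The Week 10 assessment is described as a repeat of the baseline questionnaires, and the MOS SAS is named among them.
- **Table 1.** The MOS SAS is in the pre-enrollment row for inclusion criteria. It is missing from the self-report row, which covers both baseline and Week 10.
- **Section V.E.** The Baseline Data paragraph names the MOS SAS first in the battery completed in person. Item (d) gives a one-month recall period and no time points.
- **Section VI.** The scale is listed as the self-reported adherence measure under the combined heading for Aim 3 and the Exploratory Aim. Section VI.C compares baseline with 10 weeks by a two-tailed paired t test.

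**The concern.** When patients enter a study because a score is low, that score tends to rise on the next measurement even if nothing has changed. The trial has no control arm to absorb the rise. Someone working from Table 1 and the initial-visit list alone would find one pre-treatment MOS SAS, the screening score, and might pair it with Week 10. The expected change with no effect would then be above zero. Section VI also sets a low bar for promise, since slight pre-post improvement is enough for the psychological measures and a similar test applies to other outcomes. A small artefact could then be read as benefit. Two questions follow: is the screening score really the baseline, and if it were, how much would that matter?

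**Working it through.** **Step 1: which score is the baseline?** The passages divide as follows.

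| Source | Points to |
|---|---|
| V.E, Baseline Data | MOS SAS in the in-person baseline battery |
| III.B, in-hospital recruitment | Screening MOS SAS, then baseline self-report at enrollment |
| V.A, Week 10 call | MOS SAS belongs to a set already given at baseline |
| V.A, initial-visit list | Silent on the MOS SAS |
| Table 1 | MOS SAS before enrollment only |

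V.E says the accelerometer is received with that battery, and V.A hands it out at the initial visit, so the V.E battery belongs to the initial visit. For outpatients contacted by letter, eligibility is settled earlier by telephone: "If the patient remains interested, staff will confirm eligibility and assess for exclusion criteria". An in-person MOS SAS for them is naturally a second administration.

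Table 1 cannot outweigh this. It omits the Week 10 MOS SAS that V.A requires, and the AUDIT-C that V.A gives at both visits. Its silence at baseline is the same kind of omission.

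**Step 2: the size if the screening score were used anyway.** The plan gives no MOS SAS mean, SD, correlation or total range, so there is no figure to reproduce and every input except the cutoff is an assumption.

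Let the unselected score have mean m and SD s, let r be the correlation between screening and Week 10, and assume no effect. With a cutoff of 15 on an integer score, k = (15.5 − m)/s and

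spurious gain = (1 − r) × s × φ(k)/Φ(k).

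- m = 11, s = 2, r = 0.8: k = 2.25; 0.2 × 2 × 0.0317/0.9878 = 0.013.
- m = 14, s = 3, r = 0.7: k = 0.5; 0.3 × 3 × 0.3521/0.6915 = 0.46.
- m = 15, s = 3, r = 0.5: k = 0.167; 0.5 × 3 × 0.3934/0.5662 = 1.04.

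Simulating integer scores clipped to an assumed 3 to 18 gives 0.015, 0.45 and 0.98. By unselected mean, over SD 2 to 3 and r from 0.5 to 0.8:

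| Mean | Gain (points) | Screened patients eligible |
|---|---|---|
| 11 | 0.02–0.21 | 93–99% |
| 12 | 0.04–0.34 | 88–96% |
| 13 | 0.09–0.52 | 80–89% |
| 14 | 0.17–0.73 | 69–77% |
| 15 | 0.28–0.98 | 57–60% |

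At n = 11, two-sided rejection with no effect runs from 4.7% to 20.3%. The gain exceeds one standard error of the mean change in 4 of the 40 combinations, all with mean 15 and r of 0.6 or less. These are counts of assumed cases, not probabilities.

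**Step 3: what would insisting on a repeat gain?** If the screening and repeat scores correlate at q, the gain left is (q − r) × s × φ(k)/Φ(k), so the fraction left is (q − r)/(1 − r). For mean 14, SD 3, r = 0.7, simulation leaves 0.00, 0.14, 0.29 and 0.36 of the 0.45 points at q = 0.7, 0.8, 0.9 and 0.95. The last is 0.36/0.45 = 80%. A high q is plausible: the items look back a month, and the consent wait is optional ("If they desire, participants will have at least 24 hours to consider enrollment"), so screening and baseline may fall on the same day.

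**The case for a change.** The strongest opposing case is that no sentence says outright which pre-treatment score enters the paired test. V.E names a baseline MOS SAS but does not exclude entering the screening score under that name, and item (d) gives no time points where the SSQ paragraph gives both. Staff who follow Table 1 would collect only one score. The bias would then be upward, no comparator would reveal it, and correcting the schedule costs little.

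Most of this stands as fact. The documents are inconsistent, and the direction of the conditional bias is right. What does not stand is the step to a flaw in the analysis. It needs a reading that no passage states, against three that point to a separate baseline. Its size rests wholly on assumed inputs, and the filter is meant to be mild: "We will enroll only those patients who have at least mild deficiencies in health behaviors". If 93% or more of screened patients qualify, the table caps the gain at 0.21 points on an exploratory scale. The main remedy, a baseline administration, is already in V.E.

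**Conclusion.** No change to the plan follows. The baseline in the paired test is most sensibly read as the V.E baseline score, with the screening score used for eligibility. An analyst with the whole protocol would read it that way. The omissions in Table 1 and the initial-visit list are clerical.

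If the screening score were used instead, the spurious gain would be about 0.015 to 0.98 points under the stated assumptions. The documents do not allow a narrower range, and the value may be near zero. Requiring a repeat would buy little beyond V.E, since close timing could leave much of any bias in place.

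The consequence is confined to how one exploratory scale is reported. The Exploratory Aim in Section II reads "To examine the impact of the intervention on physical activity, medication adherence, sodium intake, HF-related QoL, and generic HRQoL" and does not name the scale. Accelerometry is the primary health behavior measure and the LOT-R the primary psychological one. The move to a next trial rests on feasibility, fit with the qualitative work, and optimism or positive affect. Section VI.C disclaims power for these comparisons. It is unclear whether the low bar for medical and functional outcomes covers the MOS SAS, but an uncontrolled change in about 11 patients could not be attributed to the intervention in any case.
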